## **6.6 Lifestyle/Dietary Restrictions**

Participants should maintain a normal diet unless modifications are required to manage an AE such as diarrhea, nausea or vomiting.

Apalutamide may be taken with or without food.

### **6.6.1 Contraception and Pregnancy**

Study medications may have adverse effects on a fetus in utero. Refer to Appendix 3 for approved methods of contraception.

## **7 Reporting and Documentation of Results**

### **7.1 Evaluation of Efficacy: Antitumor Effect – Solid Tumors**

Response and progression in this study will be evaluated using the new international criteria proposed by the revised Response Evaluation Criteria in Solid Tumors (RECIST) guideline (version 1.1) [Eur J Ca 45:228-247, 2009] with use of PCWG3 criteria for assessment of new/pre-existing bone lesions. Changes in the largest diameter (unidimensional measurement) of the tumor lesions and the shortest diameter in the case of malignant lymph nodes are used in the RECIST v1.1 criteria.

#### **7.1.1 Definitions**

##### **Evaluable for toxicity**

All participants will be evaluable for toxicity from the time of their first protocol-defined treatment on C1D1.

##### **Evaluable for objective response**

Only those participants who have measurable disease present at baseline, have received at least one cycle of therapy, and have had their disease re-evaluated will be considered evaluable for response. These participants will have their response classified according to the definitions stated below. (Note: Participants who exhibit objective disease progression prior to the end of Cycle 1 will also be considered evaluable.)

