## 2.2 Primary Objective and Endpoints

Primary Objective	Endpoints	Time Frame
To determine the composite response rate (achieving one or more of the endpoints) of apalutamide plus cetrelimab.	

PSA50 (decline from baseline in serum PSA of <math>\geq 50\%</math>, confirmed by repeat measurement <math>\geq 4</math> weeks later)* AND/OR

Objective response by RECIST 1.1 criteria**

	From initiation of study treatment until discontinuation of treatment (maximum of 2 years).

\* to be considered evaluable for PSA50 response, patients must have baseline PSA level  $> 2$  ng/mL

\*\* to be considered evaluable for objective response, patients must have measurable soft tissue disease by RECIST 1.1 criteria on baseline scan assessment

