## 2.3 Secondary Objectives and Endpoints

Secondary Objective	Endpoints	Time Frame
1. To determine safety of the combination of apalutamide and cetrorelimab	
 
Proportion of participants with treatment-related AEs, as graded by National Cancer Institute Common Terminology Criteria for Adverse Events (NCI CTCAE version 5.0)
 
	From initiation of study treatment until treatment discontinuation.
2. To determine the median radiographic progression-free survival by PCWG3 criteria	
 
Median progression free survival by PCWG3 criteria.
 
	From initiation of study treatment until radiographic progression by PCWG3 criteria or death, whichever occurs first.
3. To determine the PSA50 and PSA90 response proportion.	
 
<math>\geq 50\%</math> and <math>\geq 90\%</math> decline from baseline in PSA, respectively, confirmed by repeat measurement <math>\geq 4</math> weeks after first time point*
 
	From initiation of study treatment until maximal decline in serum PSA during study treatment.
4. To determine the median PSA progression-free survival.	
 
Median PSA progression-free survival by PCWG3 criteria.
 
	From initiation of study treatment until PSA progression by PCWG3 criteria or death, whichever occurs first.
5. To determine the median overall survival.	
 
Median overall survival from date of start of protocol treatment until death from any cause.
 
	From initiation of study treatment until death from any cause. (3 years)
6. To determine the objective response rate by RECIST 1.1 criteria	
 
Objective response rate by RECIST 1.1 criteria.
 
Median duration of response
 
	From initiation of study treatment until maximal percent decline from baseline in SLD of target lesions.

\* To be considered evaluable for this endpoint, patients must have baseline PSA level  $> 2$  ng/mL.

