## 5.2 Dose Modifications and Management of Toxicity

Dose interruptions for up to 28 days are allowed. For treatment interruptions lasting > 28 days, resumption of treatment is only allowed if patients are experiencing clinical benefit and only upon approval of Principal Investigator.

If one or more agent(s) is permanently discontinued due to AE, the patient may continue to receive the other medication(s) within regimen.

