 Including complete blood cell (CBC) with differential and platelet count. All laboratory assessments have a window of +/- 3 days.

 Chemistry panel includes: sodium, potassium, chloride, bicarbonate, blood urea nitrogen (BUN)/creatinine, calcium, alkaline phosphatase (ALP), ALT/AST, total bilirubin. All laboratory assessments have a window of +/- 3 days.

 Thyroid function tests - including thyroid-stimulating hormone (TSH), with reflex free T4, total/free T3. Thyroid function tests will be performed on Day 1 of each Treatment Cycle.

 Whole Blood for peripheral immune marker assessment will be collected on C1D1 (pre-dose), C2D1 (pre-dose), C3D1 (pre-dose), and End of Treatment.

 Tumor assessment will be performed with CT Chest/Abdomen/Pelvis and whole-body bone scan during screening, C4D1 (-14d), C7D1 (-14d) and on D1 (-14d) of every 4 cycles thereafter (e.g. C11D1, C15D1). If PD by RECIST1.1/PCWG3, confirmatory scans are required ≥ 4 weeks following first scan showing progression. Lesions on chest x-ray are acceptable as measurable lesions when they are clearly defined and surrounded by aerated lung. However, CT is preferable.

 CT with contrast or MR brain is required during Screening only if history of brain metastases or clinical suspicion.

 Optional Tumor biopsy will be performed during Screening. Biopsy only required if no biopsy has previously been done. If no metastatic lesion is safely accessible to tumor biopsy, this requirement will be waived. Bone or soft tissue lesion is allowed, but soft tissue will be prioritized. If a patient has archival tissue obtained within 90 days of C1D1, and no intervening therapy between tissue acquisition and C1D1, the requirement for fresh tumor biopsy will be waived. Tumor biopsy at progression is

optional and should be the same lesion as Screening biopsy whenever feasible. Biopsy at PD also optional. Refer to Lab Manual for detail regarding tissue collection/biopsy.

 If a subject experiences a treatment-emergent rash of Grade  $\geq 2$ , consider referral to Dermatology for skin biopsy if clinically indicated per conventional (standard of care) rash management. See Section 5.4 for rash management.

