**Table 7.1 Response Criteria For Participants with Measurable Disease (i.e., Target Disease)**

Target Lesions	Non-Target Lesions	New Lesions	Overall Response	Best Overall Response when Confirmation is Required*
CR	CR	No	CR	≥4 wks. Confirmation**
CR	Non-CR/Non-PD	No	PR	≥4 wks. Confirmation**
CR	Not evaluated	No	PR	
PR	Non-CR/Non-PD/not evaluated	No	PR	
SD	Non-CR/Non-PD/not evaluated	No	SD	Documented at least once ≥4 wks. from baseline**
PD	Any	Yes or No	PD	no prior SD, PR or CR
Any	PD***	Yes or No	PD	
Any	Any	Yes	PD	

\* See RECIST 1.1 manuscript for further details on what is evidence of a new lesion.

\*\* Only for non-randomized trials with response as primary endpoint.

\*\*\* In exceptional circumstances, unequivocal progression in non-target lesions may be accepted as PD.

Note: Participants with a global deterioration of health status requiring discontinuation of treatment without objective evidence of PD at that time should be reported as "*symptomatic deterioration*." Every effort should be made to document the objective progression even after discontinuation of treatment.

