### 8.3 Analyses Plans

#### 8.3.1 Analysis Population

The safety population is defined as any patients who received at least one dose of protocol therapy on study.

The analysis population for the primary composite response endpoint includes all patients evaluable for composite response, defined as possessing either a Screening PSA  $> 2$  ng/mL and/or measurable disease by RECIST 1.1 criteria.

The analysis population for the time-to-event efficacy endpoints including progression-free survival, PSA progression-free survival, and overall survival are all patients who receive at least one dose of protocol therapy. Criteria for censoring for each of the study endpoints is listed below in Section 8.3.3.

The analysis population for correlative endpoints include all patients who receive at least one dose of protocol therapy who have evaluable correlative sample/data.

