### 8.3.3 Secondary Analysis (or Analysis of Secondary Endpoints)

Secondary Objective 1 Analysis: AEs will be recorded and severity-graded using CTCAE version 5.0. Clinically significant laboratory, physical exam, scan, and ECG abnormalities will be captured as AEs. The frequency and severity of AEs will be descriptively reported on a per-patient analysis.

Secondary Objective 2 Analysis: The median radiographic progression-free survival determined by PCWG3 criteria

Secondary Objective 3 Analysis: PSA50 and PSA90 response are defined as above, a  $\geq 50\%$  and  $> 90\%$  decline from baseline in serum PSA, respectively, confirmed by repeat measurement  $\geq 4$  weeks later. The PSA50 and PSA 90 response proportions will be reported along with 95% confidence interval for each study cohort, for the subset of PSA-evaluable patients (serum PSA  $\geq 2$  ng/mL at baseline).

Secondary Objective 4 Analysis: Median progression-free survival will be determined for each cohort as from the date of first dose of protocol-defined therapy, using Kaplan-Meier product limit method. Progression is defined as per Section 7.1.4. The first scan time point demonstrating radiographic progression requires confirmatory scans performed  $\geq 4$  weeks after first scan time point to confirm progression. Patients who discontinue treatment for reasons other than those listed above (e.g. AE, patient withdrawal) will be censored by the date of last treatment.

Secondary Objective 5 Analysis: The median overall survival along with 95% confidence interval will be determined from the date of first dose of protocol-defined therapy until death from any cause, using the Kaplan-Meier product limit method. Patients will be followed for long-term survival as outlined in the Study Procedures. Patients who withdraw from study will be censored for analysis of overall survival using the date of study withdrawal.

Secondary Objective 6 Analysis: The objective response rate and median duration of response will be reported along with 95% confidence interval, for the subset of patients with measurable soft tissue disease by RECIST 1.1 criteria.

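### Sections 7.1.1 and 8.3.3 give different denominators for the secondary objective response rate; applying 7.1.1 would drop patients never re-scanned and would be expected to raise the rate

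*Combined protocol and SAP*

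**What the plan says.** Three places bear on who counts in the ORR.

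- **Section 7.1.1 (Evaluable for objective response)** is worded as an exclusive condition. Patients need measurable disease at baseline and must also "have received at least one cycle of therapy, and have had their disease re-evaluated will be considered evaluable for response". A note adds back patients with objective progression before Cycle 1 ends.
- **Section 8.3.3 (Secondary Objective 6)** reports ORR and median duration of response "for the subset of patients with measurable soft tissue disease by RECIST 1.1 criteria". It sets no minimum treatment and no re-scan condition.
- **Section 2.2**, in a footnote to the primary endpoint, uses the same notion of evaluability but asks only for baseline status: "to be considered evaluable for objective response, patients must have measurable soft tissue disease by RECIST 1.1 criteria on baseline scan assessment".

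Section 8.3.1 defines populations for safety, the primary composite, the time-to-event endpoints and the correlatives, but none for ORR. Section 2.3 lists ORR as an endpoint without a denominator. No text ranks 7.1.1 against 8.3.3 or says how to count a measurable-disease patient with no post-baseline scan.

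**The concern.** The two rules differ for a patient with measurable disease at baseline who has no later scan. Under 8.3.3 he stays in the denominator as a non-responder; under 7.1.1 he leaves it. Such patients are likely to have left early through death, toxicity, withdrawal or clinical decline, so excluding them is not neutral.

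The plan makes this patient foreseeable. The calendar states: "Tumor assessment will be performed with CT Chest/Abdomen/Pelvis and whole-body bone scan during screening, C4D1 (-14d), C7D1 (-14d"). The first scheduled re-scan is therefore in the third month, and the End of Treatment visit (Section 6.3.3) lists no imaging. The note to Table 7.1 provides a category for "Participants with a global deterioration of health status requiring discontinuation of treatment without objective evidence of PD at that time".

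At stake is the reported ORR, a named secondary result. While both rules stand, an analyst could follow either one and choose after seeing the data.

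**Working it through.** The plan states no ORR count or denominator, so there is no ORR figure to reproduce. Its main design figure, 80.2% power for the Simon rule in Section 8.1.1, does reproduce (exact value 0.8024), and nothing below depends on it.

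**1. Window before the first scheduled re-scan.** Cycles last 28 days, so C4D1 = 1 + 3 × 28 = day 85. The 14-day allowance opens the window at day 71.

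**2. Effect of dropping patients never re-scanned.** Let M = patients with measurable disease, x = responders and k = patients never re-scanned. None of the k can be a documented responder.

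- Section 8.3.3: ORR = x/M
- Section 7.1.1: ORR = x/(M−k)
- Ratio of the two = M/(M−k), which exceeds 1 whenever k ≥ 1. The ORR itself rises whenever x ≥ 1 as well; with no responders both rules give 0%.

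**3. Illustration.** M, x and k are all assumptions. M cannot exceed 24, and it may be smaller because Section 3.3.1 also admits patients on PSA alone. With M = 16 and x = 4, exact (Clopper-Pearson) 95% intervals are:

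| k | ORR | 95% CI |
|---|---|---|
| 0 (the 8.3.3 rule) | 4/16 = 25.0% | 7.3–52.4 |
| 1 | 4/15 = 26.7% | 7.8–55.1 |
| 2 | 4/14 = 28.6% | 8.4–58.1 |
| 3 | 4/13 = 30.8% | 9.1–61.4 |
| 4 | 4/12 = 33.3% | 9.9–65.1 |

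**4. Varying M at an assumed 25% ORR.**

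| M, x | k = 1 | k = 4 |
|---|---|---|
| 12, 3 | 3/11 = 27.3% | 3/8 = 37.5% |
| 20, 5 | 5/19 = 26.3% | 5/16 = 31.3% |
| 24, 6 | 6/23 = 26.1% | 6/20 = 30.0% |

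**5. A lower response rate.** With M = 16 and x = 1, 1/16 = 6.3% becomes 1/14 = 7.1% at k = 2 and 1/12 = 8.3% at k = 4. The ratio is the same as in step 3, but the absolute shift is smaller.

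**6. The opposite direction.** The one-cycle condition could remove a responder who stopped during Cycle 1 and responded on a later scan. This is possible because Section 2.3 sets the ORR time frame as "From initiation of study treatment until maximal percent decline from baseline in SLD of target lesions", which does not end at treatment discontinuation. With M = 16, x = 4 and one such responder removed, ORR = 3/(15−k):

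- k = 0: 3/15 = 20.0% (4.3–48.1)
- k = 3: 3/12 = 25.0%, level with 8.3.3
- k = 4: 3/11 = 27.3% (6.0–61.0)

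This case should be rare, so upward bias is the expected direction but not a certainty.

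**7. Primary endpoint.** Section 8.3.1 says "The analysis population for the primary composite response endpoint includes all patients evaluable for composite response" and defines that by Screening PSA and/or measurable disease. It has no re-scan condition, so 7.1.1 does not cut the primary population.

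**The case against.** The strongest reply is that 7.1.1 is not a denominator rule. It sits among definitions, never mentions a rate, and goes on to say how the included patients' responses are classified. The analysis is specified in 8.3.3, which agrees with the footnote in 2.2. Section 8.3.3 also sets the PSA-evaluable subset for PSA50 and PSA90, for which 8.3.1 likewise gives no population. The absence of an ORR population in 8.3.1 is therefore consistent with 8.3.3 governing. This stands as a reason to prefer 8.3.3. It does not settle the matter, because 7.1.1 is an explicit, exclusive evaluability rule for this very response and no text sets it aside.

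Second, k may be small. Section 6.3.2.3 allows earlier scans when clinically indicated. Section 5.2 says that if an agent is stopped for an adverse event "the patient may continue to receive the other medication(s) within regimen". The Table 7.1 note asks for effort to document progression after discontinuation, and 7.1.1 itself retains patients with early objective progression. The bone-scan text in 7.1.4 places the first evaluation at 9 weeks (about day 63), earlier than the day 71 to 85 given by the calendar. All of this may reduce k, but none of it guarantees a scan.

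Third, the size is assumed. Section 1.6 reports adverse events leading to discontinuation in 6/27 (22.2%) on this combination, but without timing, so it gives no estimate of k. The ORRs cited in Sections 1.3 and 1.4 run from 3% to 44% across different drugs and populations, so 25% is only illustrative. At k = 1 the shift is 1.7 points (26.7 − 25.0) against an interval about 45 points wide (52.4 − 7.3). This is fair, and it limits the weight of the point.

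**Conclusion.** The inconsistency is real and the ORR denominator is not fixed in advance. If 7.1.1 is applied, patients never re-scanned are dropped and the reported ORR is expected to rise by the factor M/(M−k). For an assumed M = 16 this is 16/15 = 1.07 with one such patient and 16/12 = 1.33 with four. If 8.3.3 is applied, no bias of this kind arises.

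The conclusion on direction assumes that removal of a Cycle 1 responder is rarer than absence of a re-scan. The size rests wholly on assumed M, x and k. The effect is a shift in a descriptive secondary estimate with wide, overlapping intervals. The primary analysis, sample size, power and Simon boundaries do not change. It should be corrected because the correction is simple and removes a choice that could otherwise be made after the data are seen.

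**What to change.** In Section 8.3.3, state that the ORR denominator is all treated patients with measurable disease at baseline, and that a patient with no post-baseline tumor assessment, for whatever reason, counts as a non-responder. Bring 7.1.1 into line, or label its set a sensitivity analysis. Report the number of patients with no post-baseline scan and the reasons.

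The cost is one sentence in 8.3.3 and matching wording in 7.1.1. The reported ORR may be slightly less favourable than under 7.1.1. No design parameter changes.

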##### **Evaluable Non-Target Disease Response**

Participants who have lesions present at baseline that are evaluable but do not meet the definitions of measurable disease, have received at least one cycle of therapy, and have had their disease re-evaluated will be considered evaluable for non-target disease. The response assessment is based on the presence, absence, or unequivocal progression of the lesions.

### 7.1.2 Disease Parameters

#### Measurable disease

Measurable lesions are defined as those that can be accurately measured in at least one dimension (longest diameter to be recorded) as  $\geq 20$  mm ( $\geq 2$  cm) by chest x-ray or as  $\geq 10$  mm ( $\geq 1$  cm) with CT scan, MRI, or calipers by clinical exam. All tumor measurements must be recorded in millimeters (or decimal fractions of centimeters).

Note: Tumor lesions that are situated in a previously irradiated area considered measurable only if radiographic evidence of progression following completion of prior radiation treatment.

#### Malignant lymph nodes

To be considered pathologically enlarged and measurable, a lymph node must be  $\geq 15$  mm ( $\geq 1.5$  cm) in short axis when assessed by CT scan (CT scan slice thickness recommended to be no greater than 5 mm [0.5 cm]). At baseline and in follow-up, only the short axis will be measured and followed.

#### Non-measurable disease (Tumor Markers)

All other lesions (or sites of disease), including small lesions (longest diameter  $<10$  mm [ $<1$  cm] or pathological lymph nodes with  $\geq 10$  to  $<15$  mm [ $\geq 1$  to  $<1.5$  cm] short axis), are considered non-measurable disease. Bone lesions, leptomeningeal disease, ascites, pleural/pericardial effusions, lymphangitis cutis/pulmonitis, inflammatory breast disease, and abdominal masses (not followed by CT or MRI), are considered as non-measurable.

Note: Cystic lesions that meet the criteria for radiographically defined simple cysts should not be considered as malignant lesions (neither measurable nor non-measurable) since they are, by definition, simple cysts.

'Cystic lesions' thought to represent cystic metastases can be considered as measurable lesions, if they meet the definition of measurability described above. However, if non-cystic lesions are present in the same patient, these are preferred for selection as target lesions.

#### Target lesions

All measurable lesions up to a maximum of 2 lesions per organ and 5 lesions in total, representative of all involved organs, should be identified as target lesions and recorded and measured at baseline. Target lesions should be selected on the basis of their size (lesions with the longest diameter), be representative of all involved organs, but in addition should be those that lend themselves to reproducible repeated measurements. It may be the case that, on occasion, the largest lesion does not lend itself to reproducible measurement in which circumstance the next largest lesion which can be measured reproducibly should be selected. A sum of the diameters (longest for non-nodal lesions, short axis for nodal lesions) for all target lesions will be calculated and reported as the baseline sum diameters. If lymph nodes are to be included in the sum, then only the short axis is added into the sum. The baseline sum diameters will be used as reference to further characterize any objective tumor regression in the measurable dimension of the disease.

#### Non-target lesions

All other lesions (or sites of disease) including any measurable lesions over and above the 5 target lesions should be identified as non-target lesions and should also be recorded at baseline. It is possible to record multiple non-target lesions involving the same organ as a single item on the case record form (e.g. "multiple enlarged pelvic lymph nodes" or "multiple liver metastases"). Bone lesions may be measurable if  $\geq 1$  cm on MRI. Measurements of these lesions are not required, but the presence or absence of each will be noted throughout follow-up.

### **Non-measurable disease (Tumor Markers)**

Non-measurable disease is all other lesions (or sites of disease), including small lesions (longest diameter  $< 20$  mm with conventional techniques or  $< 10$  mm using spiral CT scan). Leptomeningeal disease, ascites, pleural or pericardial effusion, lymphangitic involvement of skin or lung, abdominal masses/abdominal organomegaly identified by physical exam that is not measurable by reproducible imaging techniques are all non-measurable.

